8.2.4. Inclusion Criteria

8.2.4.1. Feasibility Assessment

For the feasibility assessment, the individual will be included if there is at least one day of follow-up and the individual has at least 12 months of data in the data source at the index date.

8.2.4.2. SCRI Design

For analyses of outcomes assessed with the SCRI design, the following criteria must be met. Note that the study population for each outcome-specific analysis will thus be different.

- Received a dose of Ad26.COV2.S vaccine during the study period.
- Have experienced the corresponding AESI during the control or risk window (as defined in [Table 1](#))
- Have at least one day of follow-up in both the control and the risk window.
- Have at least 12 months of data/registration in the data sources prior to start of pre-vaccination control window.

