8.1.2.1. Self-controlled Risk Interval Design (Primary Study Design for Acute Events)

The SCRI design will compare the risk of the AESI in a post-vaccination risk window to a pre-vaccination control window (sensitivity analysis) and post-vaccination control window (main analysis) within the same individual.

The SCRI design will include only individuals in the primary analysis who received at least one first-ever dose of the Ad26.COV2.S vaccine during the study period. Vaccinated individuals enter the study at the date of the start of the pre-vaccination control window. The SCRI design will compare the risk of each outcome during the post-vaccination risk window following the COVID-19 dose with a self-matched control interval that may be prior to vaccination, or after the vaccination risk window, to assess the baseline risk of the outcome. The control window will have the same maximum length as the risk window to minimise time-varying confounding that cannot be measured. In case the follow-up time does not capture the maximum post-vaccination risk or control window due to right censoring, all available follow-up time will be utilized. Follow-up will be censored upon vaccination with another COVID-19 vaccine or end of follow-up. A washout period between the control and risk window will be applied to minimise capturing of prevalent events during the risk window. A post-vaccination control window may induce a bias towards the null when an AESI that was identified during the vaccination risk window, is captured again during the control window due to a re-admission instead of reoccurrence of the AESI. This situation is more likely to be encountered for acute potentially recurring events such as cardiac events (including acute coronary syndrome, myocarditis, pericarditis, arrhythmia, and stress cardiomyopathy). Moreover, due to lag-times in updating the relevant databanks, there is a higher risk that the post-vaccination control window may not capture all events and underestimate the rate of events. Use of a pre-vaccination control window will deal with these issues. In a sensitivity analyses, we will use a pre-vaccination control window and a post-vaccination control window will be used for the main analysis. In a sensitivity analysis, vaccination to other non-COVID-19 vaccines will also be an exclusion and censoring event.

We will also compare the Ad26.COV2.S vaccine with active comparators with 1) only 1-dose strategy and 2) a 2-dose strategy.

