8.2.3. Study Duration and Follow-Up

Feasibility Assessment

For the feasibility assessment, the study period will start on the date when each participating country begins with the Ad26.COV2.S vaccine or the latest date when the individual is registered in the data source (plus 365 days) or born and will end a maximum of 12 months thereafter. Individuals will be followed until the earliest of the following dates: death, end of data availability, individual exit from the data source, or the completion of the period.

Safety Evaluation Study

- For the SCRI design, the study period will start at the date of the start of the pre-vaccination control window (Table 1). Follow-up ends at the earliest of the following: death, end of data availability, individual withdrawal of the study, end of the post-vaccination risk or control window, or receipt of another COVID-19 vaccine. In a sensitivity analysis, follow-up will be censored upon receipt of other vaccines (non-COVID-19 vaccine). We will also compare the Ad26.COV2.S vaccine with active comparators with 1) only 1-dose strategy and 2) a 2-dose strategy. Figure 1 shows the different periods considered for the SCRI design.
- For the cohort design, the study period will start at the date when each participating country will begin with the Ad26.COV2.S vaccine and will end at the end of data availability at each data source. For the cohort design, the follow-up will start at the beginning of the vaccination risk window, as detailed in Table 1 and ends at the occurrence of each AESI, death, end of data availability, individual exits the database, after one year of follow-up, receipt of a

COVID-19 vaccine (unexposed cohort only), receipt of a different COVID-19 vaccine from the one granting access to the study (exposed cohorts only). For the vaccine-exposed comparator groups, a second dose of the same corresponding vaccine will be allowed (more details will be provided in the SAP). In a sensitivity analysis, follow-up in the cohort study will be censored upon receipt of other vaccines (non-COVID-19 vaccine). Another sensitivity analysis will also compare the Ad26.COV2.S with active comparators with (1) a 1-dose strategy and (2) a 2-dose strategy. For the subgroup analysis of subjects without COVID-19 at the start of risk window, patients will be censored if they develop COVID-19 during follow-up.

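### In the primary SCRI analysis, risk-window cases who die before the post-vaccination control window opens drop out, which biases the rate ratio downwards for AESIs with appreciable short-term mortality

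*Protocol*

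**What the plan says.** Four statements in the protocol combine.

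- **Control window.** Section 8.1.2.1 says that "a post-vaccination control window will be used for the main analysis". Table 5 (section 8.7) agrees for the primary analysis of acute AESIs.
- **Inclusion.** Section 8.2.4.2 requires SCRI cases to "Have at least one day of follow-up in both the control and the risk window". It does not say which control window is meant; for the main analysis the natural reading is the post-vaccination one.
- **End of follow-up.** For the SCRI, section 8.2.3 states: "Follow-up ends at the earliest of the following: death, end of data availability, individual withdrawal of the study", followed by the end of the window or another COVID-19 vaccine. The AESI itself is not listed. For the cohort design, follow-up "ends at the occurrence of each AESI, death, end of data availability", and so on.
- **Truncated windows.** Where right censoring shortens a post-vaccination window, section 8.1.2.1 says "all available follow-up time will be utilized".

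Section 8.1.3 adds a buffer between the windows, with its length left to the SAP. Section 8.7.1.3 specifies conditional Poisson regression.

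On repeat records, section 8.1.2.1 recognises that a risk-window AESI may be one that "is captured again during the control window due to a re-admission instead of reoccurrence of the AESI", and calls this a bias towards the null. After also naming data lag, it concludes: "Use of a pre-vaccination control window will deal with these issues". That window is used only in a sensitivity analysis (sections 8.1.2.1 and 8.7.6).

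**The concern.** A self-controlled comparison needs the observation time to be unrelated to the event. Here it is not. If the risk-window event is fatal, the person usually has no control time and is lost. If the control-window event is fatal, the person has by definition already completed the risk window, so the case is kept and only the control time is shortened. Risk-window cases are lost and the control-window rate is raised, so both effects lower the rate ratio.

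The outcomes most exposed are those that can kill quickly, such as thrombosis with thrombocytopenia, stroke, pulmonary embolism and acute coronary syndrome. Thrombosis with thrombocytopenia is an identified risk that the background section gives as a reason for surveillance. In a safety study, an error that shrinks a real excess is the costly kind. Neither section 8.1.2.1 nor the limitations in section 8.9 mentions this loss.

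The readmission issue is secondary. The protocol discloses it, but the main analysis has no stated rule that removes it.

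**Working it through.** **1. The plan's own power figure.** With equal windows, b = ln(RR) and p = RR/(RR+1), the signed-root formula is:

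- A = 2[p·b − ln((RR+1)/2)]
- B = (b²/A)·p(1−p)
- power = Φ((√(nA) − 1.96)/√B)

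Two-sided alpha of 0.05 is assumed; the protocol gives only 95% intervals. For RR 2 and n = 100: A = 0.1133, B = 0.943, and power = Φ((3.366 − 1.96)/0.971) = 92.6%. This matches Table 3.

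**2. Loss of fatal risk-window cases, closed form.** Let f be the share of risk-window cases who die before the control window opens. Then RR_obs = RR(1 − f). The 100 events at RR 2 split into 66.7 in the risk window and 33.3 in the control window.

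| f | Risk / control events | RR_obs | Power |
|---|---|---|---|
| 0 | 66.7 / 33.3 | 2.00 | 92.6% |
| 10% | 60.0 / 33.3 | 1.80 | 79.9% |
| 20% | 53.3 / 33.3 | 1.60 | 58.0% |

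**3. Full mechanism, by simulation of the conditional Poisson estimator.** The windows are 28 days, as in Table 1 for most of the thrombotic outcomes. Three inputs are assumptions, because the protocol does not give them: a 14-day gap, exponential time from event to death with mean 5 days, and the fatality itself. Under these inputs the share of fatal risk-window cases still alive when the control window opens is (5/28)(e^(−14/5) − e^(−42/5)) = 1.1%, so nearly all are lost. Fatal control-window cases are kept with control time cut at death.

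| Short-term fatality | True RR 2 | True RR 1 |
|---|---|---|
| 5% | 1.89 | 0.94 |
| 10% | 1.77 | 0.88 |
| 20% | 1.55 | 0.75 |
| 40% | 1.10 | 0.52 |

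At 2% fatality a true RR of 2 becomes 1.95. A mean of 7 days to death, or no gap at all, moves the RR 2 results by less than 0.05. A mean of 30 days at 10% fatality gives 1.85. Fatality is the main driver.

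**4. Which rule does the damage.** Removing only the one-day criterion leaves the estimate at 1.77 (RR 2, fatality 10%), because a case with no control time adds nothing to a conditional likelihood. Giving every case its planned control window returns 2.00 and 1.00 at all fatality levels.

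**5. Readmissions.** Let g be the assumed share of risk-window cases recorded again in the control window. Then RR_obs = RR/(1 + g·RR).

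- RR 2: g = 10% gives 2/1.2 = 1.67, and g = 20% gives 2/1.4 = 1.43.
- RR 1: g = 10% gives 1/1.1 = 0.91, so the bias is downwards rather than strictly towards the null.
- With the pre-vaccination order, a readmitted control-window case can fall in the risk window. If the same share g is re-recorded there, RR_obs = RR + g, for example 2.10 for g = 10%, unless the gap absorbs it.

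**The case against.** Several counter-arguments have weight.

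- **Planned checks exist.** The pre-vaccination SCRI and the matched cohort analysis of acute events both keep fatal risk-window cases, so a discrepancy could be seen. This stands, but both are sensitivity analyses and the primary estimate stays biased. The pre-vaccination order also has its own survival problem: a person who dies of an AESI in that window is never vaccinated and never enters. The two orders therefore do not isolate the bias cleanly.
- **The choice of window is reasoned.** The summary of changes cites the healthy vaccinee effect. That supports the post-vaccination window; it does not require control time to stop at death.
- **Most acute AESIs are rarely fatal.** A reader might infer that every acute AESI is materially biased. The figures do not support that: for Bell's palsy, hearing loss or similar outcomes the effect is negligible.
- **Net direction.** A reader might infer that the whole analysis is biased downwards. Section 8.1.2.1 also names data lag, which undercounts control events and raises the ratio. Only the two mechanisms here have a known sign.
- **Readmissions.** A reader might infer that the protocol instructs repeats to be counted. It does not. It gives no first-event rule, and the SAP may supply one. The gap between windows also removes some early repeats. The sentence on the pre-vaccination window is partly right, since an earlier control window does help with data lag.

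**Conclusion.** The death mechanism follows from stated rules, is not disclosed, and sits in the primary analysis. For AESIs with short-term fatality of 5 to 20%, a true ratio of 2 would be estimated at about 1.89 to 1.55. Only at an assumed 40% does it approach 1. The size rests on the assumed fatality and, much less, on the assumed gap and time to death; none of these is in the protocol. Deaths unrelated to the AESI cause no such bias. The cause is the combination of a later control window with follow-up ending at death, not the inclusion criterion alone. The readmission issue is a lesser point of wording: it is acknowledged, but the primary analysis has no stated remedy.

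**What to change.** 1. In sections 8.2.3 and 8.1.2.1, for the SCRI with a post-vaccination control window, state that when death follows the AESI the observation period runs to the planned end of the control window, not to the date of death. Keep censoring at end of data and at the next COVID-19 vaccine.
2. Reword the criterion in section 8.2.4.2 so that these cases are included. This works only together with step 1.
3. State in sections 8.1.2.1 and 8.7.1.3 that only the first AESI after the washout, across the risk and control windows, is counted.
4. In section 8.1.2.1, limit the claim for the pre-vaccination window to data lag.
5. Align the abstract, and mention the issue in section 8.9.

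The cost is protocol and SAP wording and a small change to case-selection code, with no new data. Step 1 relies on deaths from other causes being rare within the short windows. With an assumed unrelated death hazard of 0.0005 per day, the simulation with planned windows gave 2.04 for a true ratio of 2 and 1.02 for a true ratio of 1, much less than the bias removed for outcomes with appreciable fatality.

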8.2.4.3. Cohort Design

Individuals must meet all the following inclusion criteria to be eligible for inclusion in the cohort study:

- Have received their first-ever dose of the corresponding COVID-19 vaccine within the study period
- Had at least 12 months of data available before the index date or were born in the previous 12 months and have been enrolled since birth

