[Figure 1](#) shows the SCRI study design diagrammatically using an example with a risk window and control window of 42 days.

Figure 1: Self-Controlled Risk Interval Design

T is time and T=0 is the index date.

8.1.2.2. Cohort Design (Primary Study Design for Non-acute Events and Sensitivity Analysis Design for Acute Events)

For the primary analysis of non-acute events, a retrospective cohort design will be used to estimate the rate of vaccination with Ad26.COV2.S vaccine, describe the characteristics of these vaccinated individuals and subsequently to estimate the incidence of new-onset autoimmune thyroiditis, multiple sclerosis, acute aseptic arthritis, and type 1 diabetes mellitus after receipt of the vaccine dose and to compare this incidence with that occurring in an unvaccinated matched comparator group, and in two groups of individuals exposed to other types of COVID-19 vaccines (i.e., one viral vector vaccine comparator group vaccinated [i.e., Vaxzevria[®] {AZD1222}] by Oxford/AstraZeneca) and one mRNA vaccine comparator group (i.e., Comirnaty[®] [tozinameran] by Pfizer/BioNTech and Spikevax[®] [elasomeran] by Moderna).

As a sensitivity analysis for acute events, a cohort analysis (following the same approach used in the main analysis for non-acute events) will be conducted.

- **Exposed cohort:** individuals will have received at least 1 dose of Ad26.COV2.S vaccine.
- **Concurrent unexposed cohort:** individuals that have not been vaccinated with Ad26.COV2.S vaccine or any other COVID-19 vaccine at any time prior to the index date (time zero) matched to the vaccinated individual for important characteristics as described in Section 8.7.2.1.
- **Cohort exposed to other COVID-19 vaccines:** individuals will have received at least 1 dose of a viral vector COVID-19 vaccine (i.e., Vaxzevria[®] [AZD1222] by Oxford/AstraZeneca) or an mRNA COVID-19 vaccine (Comirnaty[®] [tozinameran] by Pfizer/BioNTech and Spikevax[®] [elasomeran] by Moderna, respectively).

A sensitivity analysis will compare the Ad26.COV2.S vaccine with the active comparators with 1) a 1-dose strategy and 2) a 2-dose strategy.

In this retrospective cohort design, the start of follow-up will be defined as the time when study outcomes start to be counted. The index date in the exposed cohorts (i.e., recipients of the vaccines)

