will be the day the first dose of the corresponding COVID-19 vaccination was received. This date in the unexposed group will be a day when an individual did not receive a COVID-19 vaccine dose and randomly chosen by calendar matching to the start date of the corresponding Ad26.COV2.S exposed individual (i.e., a random day during the same week that the matching individual in the exposed cohort receives the Ad26.COV2.S vaccine).

Individuals in the Ad26.COV2.S exposed cohort will be individually matched to one individual in the concurrent unexposed cohort and to one individual in each active comparator cohorts on key clinical variables (exact age, sex, previous COVID-19 infection and presence of one or more risk factors for severe COVID-19 [e.g., cancer, sickle cell disease, obesity, chronic kidney disease, chronic respiratory disease, human immunodeficiency virus infection], and month of vaccination (using calliper if needed)) at the index date.

[figure not shown]
Three sets of matched cohorts of individuals who meet all inclusion and exclusion criteria will be considered as follows:

- Recipients of a first Ad26.COV2.S dose matched to recipients of the first dose of a viral vector COVID-19 vaccine (AstraZeneca vaccine)
- Recipients of a first Ad26.COV2.S dose matched to recipients of the first dose of an mRNA COVID-19 vaccine (Pfizer-BioNTech or Moderna)
- Recipients of a first Ad26.COV2.S dose matched to unvaccinated individuals at the index date (individuals in this cohort may later become eligible to enter the exposed cohorts if vaccinated with a COVID-19 vaccine).

For the matched exposed cohorts, the index date (time zero) will be the date of the corresponding COVID-19 vaccine. For the unvaccinated individuals, the index date will be assigned as the index date of the matched exposed individual (see [Figure 2](#)). Additional details regarding matching will be included in the SAP.

Follow-up for unexposed persons is censored when the individual receives a COVID-19 vaccine. In a sensitivity analysis, vaccination with other non-COVID-19 vaccines will also be an exclusion and censoring event.

Figure 2: Schematic Overview of the Cohort Study Design

AESI = adverse event of special interest; COVID-19 = coronavirus disease 2019; FU = follow-up; SARS-CoV-2 = severe acute respiratory syndrome coronavirus-2.

Note: In the figure 1 year enrolment refers to the inclusion criterion to have at least 12 months of data available before the index date.

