- Individuals who receive the first dose of the Ad26.COVS.S vaccine will be classified as exposed to Ad26.COVS.S vaccine. Individuals will be censored if and when they receive a non-Ad26.COVS.S COVID-19 vaccine during follow-up. Individuals who receive a second dose of Ad26.COVS.S vaccine will also be censored at the date of that dose as this is not the current dosing schedule. When the dosing schedule changes for Ad26.COVS.S vaccine, the study protocol may be amended.

- The vaccination strategy for the matched unexposed group will be defined as not receiving a COVID-19 vaccine of any brand during the follow-up period. Individuals will be censored when they receive a dose of any COVID-19 vaccine during the observation period.
- The vaccination strategy for the matched groups receiving other COVID-19 vaccines will be defined as 1) receiving a viral vector COVID-19 vaccine (i.e., Vaxzevria[®] [AZD1222] by Oxford/AstraZeneca) or 2) receiving a mRNA COVID-19 vaccine (i.e., Comirnaty[®] [tozinameran] by Pfizer/BioNTech or Spikevax[®] [elasomeran] by Moderna). Individuals will be censored when they receive a dose of a COVID-19 vaccine of a different type during the observation period (e.g., a patient with the first dose of AZD1222 receives a second dose with a mRNA COVID-19 vaccine).

For the SCRI design, person-time in the risk interval will be considered “exposed” while person-time in the control interval will be considered “unexposed.” Risk intervals are specific to the outcome of interest.

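### The cohort inclusion criteria in 8.2.4.3 require a vaccine dose of every member, which contradicts the definition of the unexposed cohort

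*Protocol*

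**What the plan says.** Section 8.2.4.3 opens the cohort eligibility list with "Individuals must meet all the following inclusion criteria to be eligible for inclusion in the cohort study". The first item is "Have received their first-ever dose of the corresponding COVID-19 vaccine within the study period"; the second concerns 12 months of prior data. Nothing is reserved for one cohort or another.

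Section 8.1.2.2 extends the list to the matched sets: "Three sets of matched cohorts of individuals who meet all inclusion and exclusion criteria will be considered as follows". The third of those sets pairs Ad26.COV2.S recipients with people unvaccinated at the index date.

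The unexposed cohort is described differently elsewhere:

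- Section 8.1.2.2 (and the Abstract in nearly the same words) defines it as "individuals that have not been vaccinated with Ad26.COV2.S vaccine or any other COVID-19 vaccine at any time prior to the index date".
- Section 8.1.2.2 adds that "individuals in this cohort may later become eligible to enter the exposed cohorts if vaccinated with a COVID-19 vaccine".
- Section 8.3.1 states: "The vaccination strategy for the matched unexposed group will be defined as not receiving a COVID-19 vaccine of any brand during the follow-up period".
- Section 8.1.2.2 sets the censoring rule: "Follow-up for unexposed persons is censored when the individual receives a COVID-19 vaccine".

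According to 8.2.3, the cohort study period "will end at the end of data availability at each data source".

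**The concern.** The eligibility list and the design description cannot both be followed for the unexposed cohort. A person who never receives a COVID-19 vaccine is the plainest example of an unexposed comparator, yet fails the first inclusion criterion. Someone unvaccinated at the index date can satisfy it only through a dose given afterwards.

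If the list were applied as written, membership of the comparator group would depend on something that happens after time zero. Exposed-versus-concurrent-unexposed is a primary comparison for non-acute AESIs and is also used in the cohort sensitivity analysis for acute AESIs (8.1.2 and Table 5). Section 8.6.2 has the scripts written centrally and sent to each data access provider, so a literal implementation would affect every data source in the same way.

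**Working it through.** No stated figure is at issue, so the main check is to test the clauses against two kinds of people.

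| Clause | Never vaccinated | Unvaccinated at index, vaccinated later |
|---|---|---|
| 8.1.2.2, no vaccine before index date | meets | meets |
| 8.1.2.2, later vaccination optional | meets | meets |
| 8.3.1, no vaccine during follow-up, otherwise censored | meets; contributes time for up to a year | meets until the dose, then censored |
| 8.2.4.3, first-ever dose within the study period | **fails** | meets, through the later dose |
| 8.1.2.2, matched sets must meet all criteria | **fails** | meets |

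**Step 1: is there an exemption elsewhere?** The exclusion criteria in 8.2.5 do not provide one. They bar people vaccinated with any *other* COVID-19 vaccine before the risk window, which has no clear referent for someone with no vaccine. Sections 8.2.4.3 and 8.2.5 therefore contain no workable entry rule for the unexposed.

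**Step 2: does the criterion look past the index date?** Yes. The study period runs to the end of data availability (8.2.3), so a dose well after the index date satisfies it.

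**Step 3: what follows if it is applied literally?** Every unexposed member must be alive and registered at the later dose. Their unexposed follow-up ends at or before that dose, so it cannot be ended by death or by leaving the database. An AESI is counted only in someone who goes on to be vaccinated. This is conditioning on a future event, with immortal time.

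**Step 4: can the direction be determined?** Incidence rates are events divided by person-time (8.7.1.2). Restricting the unexposed group to later vaccinees therefore changes both parts:

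observed IRR / true IRR = (share of unexposed person-time kept) / (share of unexposed events kept).

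The documents give neither share. The following inputs are assumptions, used only to show that the sign is open:

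- 10% of unexposed people are never vaccinated.
- 30% of unexposed events occur among them, so 70% of events are kept.
- The never-vaccinated contribute 365 days, the maximum in 8.2.3.
- Later vaccinees contribute a mean of 60 days before censoring.

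Person-time per head of the full unexposed group:

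- Later vaccinees: 0.90 × 60 = 54 days.
- Never-vaccinated: 0.10 × 365 = 36.5 days.
- Share kept: 54 / 90.5 = 0.60.

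The ratio is 0.60 / 0.70 ≈ 0.85, so a true IRR of 1.0 would read about 0.85.

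The sign changes where 0.90t / (0.90t + 36.5) = 0.70. This gives 0.27t = 25.55, so t ≈ 95 days. With the other inputs held, the IRR is biased downwards if later vaccinees average less than about 95 days of follow-up, and upwards if they average more.

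**The case against.** The strongest reply is that the criterion was never meant for the unexposed. It speaks of the *corresponding* vaccine, and 8.1.2.2 uses the same word when fixing the index date for vaccine recipients; an unexposed person has no corresponding vaccine. The definition, the optional later vaccination and the strategy in 8.3.1 all point to a cohort that includes people who stay unvaccinated. Most of the missing criterion already appears in 8.1.2.2.

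This stands as evidence of intent. It does not remove the conflict, because 8.1.2.2 itself requires the unvaccinated matched set to meet all the inclusion criteria, and 8.2.4.3 says all must be met without exception. The SAP, which is not at hand, may state the rule correctly; the protocol would still state it wrongly.

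Two stronger readings are tempting, and the documents support neither:

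- **That the sponsor plans to exclude the never-vaccinated.** No passage says so, and several imply the opposite.
- **That the IRR is biased upwards, by a factor of about 1.29.** A reader could reach this by counting heads: 0.90 / 0.70 = 1.29. That uses the same unsupported 10% and 30% and treats the share of people kept as the share of person-time kept. This would hold only if later vaccinees and the never-vaccinated had equal mean follow-up, whereas the former are censored at their dose. Nor do the documents show that autoimmune thyroiditis, multiple sclerosis, aseptic arthritis or type 1 diabetes deters later vaccination; 8.3.1 lists risk group as an example of a recorded reason for vaccination in SIDIAP, which could work the other way.

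**Conclusion.** The point holds as an internal contradiction in the eligibility text. As written, 8.2.4.3 excludes never-vaccinated people and admits unexposed comparators only through a later dose, against 8.1.2.2 and 8.3.1. It is most probably a drafting error.

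The contradiction rests on the wording alone and needs no assumption. The consequence, selection on a future event in a primary comparison for non-acute AESIs, arises only if the criterion is implemented literally. Neither direction nor size can then be stated: under the assumed inputs above, moving the mean follow-up of later vaccinees from 60 to 365 days takes a true IRR of 1.0 from about 0.85 to 1.29. That span shows the sign is open; it is not an estimate of the bias.

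**What to change.** In 8.2.4.3, limit the first criterion to the Ad26.COV2.S and active-comparator cohorts. Add a criterion for the concurrent unexposed cohort: no record of any COVID-19 vaccine on or before the assigned index date, regardless of later vaccination. The 12-month data criterion can stay common to all cohorts, and the sentence in 8.1.2.2 about the matched sets then needs no change.

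The cost is two sentences in the protocol and a check that the SAP and the central scripts apply the same rule. The intended design, the data needed and the study size calculation are unaffected.
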